6.7.1 Comparison to Operating Characteristics of Original Design

Table 5 displays corresponding operating characteristics of the original design (with a maximum of N=120 subjects). In comparing Table 4 and Table 5, it is clear that the stopping probabilities at N=60, 75, and 90 have not changed, and the probability of stopping at N=105 in Table 4 is the sum of the probabilities of stopping at N=105 and N=120 in Table 5. For example, in the first row, Table 4 shows a probability = 0.1403 of stopping enrollment at N=105, which is the sum of 0.0617 + 0.0061 + 0.0725 (entries in the N=105 and N=120 columns in Table 5). The Average N in Table 5 tends to be slightly smaller. The observed power (i.e. Type I error rate) is not meaningfully different (0.0260 and 0.0253 in Table 4, 0.0260 and 0.0246 in Table 5).

Table 5 Operating Characteristics of the Original Design with Varying Accrual Rates

ϕ^*	Power	Average N	Probability for Stopping Enrollment (by Reason)				
			At N=60 (Promise, Futile)	At N=75 (Promise, Futile)	At N=90 (Promise, Futile)	At N=105 (Promise, Futile)	At N=120 (Max)
Slower Accrual Rate (3/month) – Null Scenario							
0.54	0.0260	74.7	0.4978	0.2245	0.1241	0.0617	0.0725
			0.0044	0.0038	0.0051	0.0061	
Faster Accrual Rate (7/month) – Null Scenario							
0.54	0.0246	78.2	0.4020	0.2503	0.1543	0.0790	0.0956
			0.0038	0.0035	0.0051	0.0064	

7 SECONDARY ENDPOINTS ANALYSIS

A listing of secondary endpoints is given in Section 3.2. Secondary endpoints will be evaluated with descriptive statistics, along with 95% confidence intervals computed using frequentist methods. No hypothesis tests will be conducted.

Methods:

- Secondary endpoints that are binary (e.g., technical success, freedom from contrast-induced nephropathy at 72 hours) will be summarized as a proportion, with a 95% confidence interval computed via an exact binomial calculation.

STATISTICAL ANALYSIS PLAN

- Secondary endpoints that involve the occurrence (or not) of events at times ≥ 30 days will be summarized with Kaplan-Meier time-to-event methods. Confidence intervals will be computed on the log(survival) scale.
- Continuous endpoints (e.g., procedure time, radiation exposure, contrast volume) will be summarized with means, medians, SD, quartiles, min, and max. Confidence intervals will be computed assuming approximate normality.

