3.2 Secondary Objectives

The secondary objectives consist of determining the test device's point estimate and its precision for the following endpoints:

- **Primary Patency:** Defined as the absence of occlusion of the endovascular intervention maintained with no additional or secondary surgical or endovascular procedures, at 30 days and 6 months.
- **Primary Assisted Patency:** Defined as the absence of occlusion of the endovascular intervention maintained with using additional or secondary surgical or endovascular procedures, as long as occlusion of the primary treated site has not occurred, at 30 days and 6 months.

STATISTICAL ANALYSIS PLAN

- **Secondary Patency:** Defined as the absence of occlusion of the endovascular intervention maintained with using additional or secondary surgical or endovascular procedures after occlusion occurs, at 30 days and 6 months.
- **Limb Salvage:** Defined as the percentage of subjects with freedom from above-ankle amputation of the index limb, evaluated at 30 days, 3 and 6 months.
- **Change in Rutherford Classification:** Defined as a change of one class or greater, as evaluated at 30 days, 3 and 6 months.
- **Technical Success:** Defined as successful placement of the arterial and venous catheters in the desired location in the limb, ability to place the stent-grafts, completion of the endovascular procedure, and immediate morphological success.
- **Procedural Success:** Defined as the combination of technical success, and absence of all-cause death, above-ankle amputation or clinically driven major re-intervention of the stent-graft at 30 days.
- **Target Wound Healing:** Defined as complete healing of the patient's target wound as evaluated at 30 days, 3, 6, 9 months, and 1 year.
- **All Wound Healing:** Defined as complete healing of the patient's wounds as evaluated at 30 days, 3, 6, 9 months, and 1 year.
- **Freedom from Contrast-Induced Nephropathy:** Defined as subjects without acute (within 72 hours after intravenous contrast administration) impairment of renal function, measured as an absolute ≥ 0.5 mg/dL (44 μ mol/L) increase compared to baseline SCr value.
- **Procedure Time:** Defined as the time of the first puncture (venous or arterial) to when the last catheter is removed.
- **Radiation Exposure:** Defined as patient radiation exposure (in milligray) during the procedure.
- **Contrast Volume:** Defined as the total volume of contrast media (in milliliters) given during the procedure

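### SAP 7, on its natural reading, analyses wound healing and Rutherford change by Kaplan-Meier, which estimates ever healed or ever changed and not the visit status that SAP 3.2 defines

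*SAP*

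**What the plan says.** SAP section 7 has two rules that matter here. The first reads: "Secondary endpoints that are binary (e.g., technical success, freedom from contrast-induced nephropathy at 72 hours) will be summarized as a proportion", with an exact binomial interval. The second reads: "Secondary endpoints that involve the occurrence (or not) of events at times ≥ 30 days will be summarized with Kaplan-Meier time-to-event methods". The second rule lists no endpoints. The section also states: "No hypothesis tests will be conducted".

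SAP section 3.2 defines the endpoints concerned:

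- For the target wound, the text is "Defined as complete healing of the patient's target wound as evaluated at 30 days, 3, 6, 9 months, and 1 year".
- For healing of every wound, the same definition is used, without the restriction to the target wound and at the same five visits.
- For Rutherford class, the text is "Defined as a change of one class or greater, as evaluated at 30 days, 3 and 6 months".

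None of these definitions gives an event date, a minimum duration, or a rule for a wound that reopens or a class that reverts. The Rutherford definition does not say whether change means improvement, worsening or either.

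Four protocol sections also bear on the point. Section 4.10.3 has the core laboratory review healing, including its confirmation, but gives no recurrence rule. Section 5.9 exits subjects at major amputation or death. Section 11.5.1 computes proportions on non-missing values. Table 1 schedules wound assessment and Rutherford class at every visit these endpoints need.

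**The concern.** Kaplan-Meier in its ordinary form records one event per subject, the first, and treats it as permanent. That suits death or amputation. It does not suit a status that can be gained and lost. A wound closed at 3 months and open again at 6 months is not healed at 6 months under SAP 3.2, yet it stays in the healed fraction of a Kaplan-Meier curve. A Rutherford class that differs from baseline at 30 days and is back at baseline by 3 and 6 months shows no change at 6 months by definition, yet it counts as changed on the curve.

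The published healing and Rutherford percentages would then answer a different question from the one the endpoints pose, and in the direction that flatters healing. Protocol section 10.1 rests its benefit argument largely on wound healing. The trial has one arm, so no control group would carry the same inflation. The percentages would be read on their own.

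**Working it through.** **Step 1. Which rule applies.** Both examples under the binary rule, technical success and nephropathy at 72 hours, are settled before 30 days. The Kaplan-Meier rule starts at 30 days. Read together, the bullets split the endpoints at 30 days. Healing and Rutherford change are first read at 30 days, so they fall on the Kaplan-Meier side. This is an inference, because the SAP does not name them.

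**Step 2. Direction of the difference.** Let H(t) indicate healed at visit t. The endpoint is P[H(t) = 1]. First-event Kaplan-Meier, without censoring, gives P[H(u) = 1 at some visit u ≤ t]. The first set lies inside the second, so with complete follow-up Kaplan-Meier is never lower. The gap is the share who were healed at some earlier visit and are not healed at t. The same holds for Rutherford change.

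**Step 3. Size for healing.** The plan has no figure to reproduce, and every input here is an assumption. First closure is observed at 30 days, 3, 6, 9 and 12 months in f = 8%, 14%, 18%, 12% and 8% of subjects. Kaplan-Meier then reads 8 + 14 + 18 = 40% at 6 months, and 40 + 12 + 8 = 60% at 12 months. Let r be the chance that a closed wound reopens by the next visit, and q the chance that a reopened wound re-closes by the next visit. For a wound first closed j visits ago,

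s(0) = 1, s(j+1) = s(j)(1 − r) + [1 − s(j)]q,

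and status at visit v is the sum over k ≤ v of f(k) × s(v − k). There is no death or dropout.

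Example with r = 5%, q = 0, at 6 months: 0.08 × 0.95² + 0.14 × 0.95 + 0.18 = 0.385.

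Example with r = 15%, q = 0.5, at 12 months: s(1) to s(4) = 0.850, 0.798, 0.779, 0.773. Status = 0.08 × 0.773 + 0.14 × 0.779 + 0.18 × 0.798 + 0.12 × 0.850 + 0.08 = 0.496.

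| r | q | Status 6 m (Kaplan-Meier 40%) | Excess, points | Status 12 m (Kaplan-Meier 60%) | Excess, points |
|---|---|---|---|---|---|
| 5% | 0 | 38.5% | 1.5 | 54.2% | 5.8 |
| 15% | 0 | 35.7% | 4.3 | 44.0% | 16.0 |
| 5% | 0.5 | 38.7% | 1.3 | 56.2% | 3.8 |
| 15% | 0.5 | 36.3% | 3.7 | 49.6% | 10.4 |

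A second model used exponential times to healing and to reopening, no re-closure, 30-70% healing by 12 months and 10-30% reopening within 180 days of healing. Simulated in 400,000 subjects, it gave a 12-month excess from 29.3 − 26.9 = 2.4 points to 64.8 − 46.2 = 18.6 points. With no reopening the excess was zero.

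**Step 4. Rutherford change.** As a worst case, suppose no true change and independent misreadings with probability p at each of three visits. Status at 6 months shows p. Kaplan-Meier shows 1 − (1 − p)³, which is 8.7%, 14.3% and 27.1% for p = 3%, 5% and 10%. This shows the mechanism and is not a forecast.

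**Step 5. The denominator matters too.** Suppose 38 of 100 subjects are healed at 6 months and 30 have exited through death or major amputation, in line with the planning AFS of 0.70 in SAP 6.3. Over all subjects the proportion is 38/100 = 38%. Over non-missing values only, as in protocol 11.5.1, it is 38/70 = 54%. A visit proportion with no denominator rule could therefore mislead by more than the reversal effect at 6 months. Kaplan-Meier that censors at exit shares this weakness.

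**The case against.** **The method is not clearly assigned.** SAP 7 names no endpoint under Kaplan-Meier, and healed or not healed at a visit is binary, so the binary rule could apply. A class difference is not obviously an event. This has some force: the assignment is the likelier reading, not a certainty. But if proportions were intended, the text does not say so, and the same edit settles it.

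**The endpoints are only descriptive.** This stands. No success criterion, error rate or sample size depends on them, and individual listings will be provided.

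**Core-laboratory confirmation may screen out brief closures.** It may reduce them. It sets no duration and says nothing about a wound that reopens after confirmed closure.

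**The size depends on assumptions.** This also stands. The larger 12-month range needs reopened wounds never to re-close, and the 6-month excess is small in every row of the table. The direction does not depend on the rates.

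**A reader might infer that secondary patency has the same fault in reverse**, with reopened grafts counted as lost and the curve collapsing onto primary assisted patency. The documents do not support that. SAP 3.2 describes secondary patency as "Defined as the absence of occlusion of the endovascular intervention maintained with using additional or secondary surgical or endovascular procedures after occlusion occurs", so a reopened graft is still patent and the matching event is unrestored loss. Kaplan-Meier handles that event coherently. A downward bias would require first occlusion to be coded as the event, which SAP 7 does not say and which would contradict the definition. What remains is that the event is not spelled out.

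**Conclusion.** The point holds for target wound healing, all wound healing and Rutherford change. On the natural reading of SAP 7, the planned estimate is *ever by visit t*, while SAP 3.2 defines *status at visit t*. Neither document has a rule for reversal.

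For healing at 12 months the excess is about 4-10 points if half of reopened wounds re-close by each next visit, and 6-16 points if none do. Both ranges assume 60% ever closing, 5-15% reopening between visits and complete follow-up. At 6 months the excess is about 1-4 points. For Rutherford change no realistic size can be given from the documents.

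The effect is confined to descriptive secondary estimates. It should not be read as touching the AFS test or its type I error, or as showing a bias in secondary patency. It is worth correcting because it is cheap and because the healing percentages have no comparator.

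**What to change.** In SAP section 7:

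1. Take target wound healing, all wound healing and Rutherford change out of the Kaplan-Meier bullet. Report status at each scheduled visit as a proportion with an exact binomial 95% interval.
2. State the denominator, for example all mITT subjects, with death or major amputation before the visit counted as not healed or not improved. Give a rule for missed visits. Say that this replaces the non-missing rule of protocol 11.5.1 for these endpoints.
3. State the direction of Rutherford change.
4. Time to first healing may stay as a supplement, labelled as such.
5. Leave secondary patency under Kaplan-Meier. As a clarification only, state that its event is loss of patency that is not restored.

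The cost is a short SAP revision and simple tables. No new data are needed, because Table 1 of the protocol already schedules these assessments. The downsides are somewhat lower healing percentages and a missed-visit rule that must be agreed before the data are seen.

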### 5.9 Study Exit or Premature Withdrawal

Subjects will be exited from the study by completion of a Study Exit eCRF. Subjects will be exited upon completion of the follow-up visits, withdrawal of consent, or instance of meeting a primary study endpoint (major amputation or death). Following study exit, the subject will undergo the standard medical care for their condition as determined necessary and appropriate by their physician.

Subjects may be prematurely exited or withdrawn from the study for, including but not limited to, the following reasons:

- Voluntary withdrawal – meaning that the subject voluntarily chooses not to further participate in the study
- Lost to follow-up – meaning that the subject is more than 14 days out of window of a study visit and 3 documented attempts to contact the subject are unsuccessful. A subject who misses two consecutive study visits, including phone contact, will be considered lost to follow-up. A missed visit will be considered a protocol deviation and the deviation will be documented and reported.
- In the physician’s opinion, it is not in the best interest of the subject to continue study participation.

All subjects enrolled (including those withdrawn or lost to follow-up) shall be accounted for and documented.

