11.5 Statistical Analyses

11.5.1 General Approach

Descriptive statistics for continuous variables will include mean, standard deviation, median, quartiles, minimum, maximum, and sample size for each treatment group. Categorical variables will be summarized using counts and percentages. Proportions will be calculated using known non-missing values. Unless otherwise indicated, all statistical tests will be performed at  $\alpha=0.05$  (2-sided), and confidence/credible intervals will be at level 95%.

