6.3 Sample Size Considerations

Although the analysis methods are Bayesian, the following frequentist scenarios are used to guide the determination of minimum and maximum sample size.

- According to PASS 13³, when using $\alpha = 0.025$ (one-sided) in an exact binomial test, achieving 90% power to test the hypotheses in Section 6.1 when the true AFS = 0.70 would require a sample size of 101 subjects. Allowing for 10% missing data would require a sample size of N=113 subjects
- If the true AFS = 0.68, a sample size of 101 subjects would achieve 81% power. Allowing for 10% missing data would require a sample size of N=113 subjects

³ PASS 13 Power Analysis and Sample Size Software (2014). NCSS, LLC. Kaysville, Utah, USA, ncss.com/software/pass

STATISTICAL ANALYSIS PLAN

- If the true AFS = 0.75, 90% power requires a sample size of N=56 subjects. Allowing for 10% missing data would require a sample size of N=63 subjects.

There is considerable uncertainty in the true AFS rate ϕ . Consequently, it is desirable to utilize a study design that achieves at least 80% power when AFS ≥ 0.68 and 90% power when AFS ≥ 0.70 , while allowing early stopping of enrollment if the AFS rate proves to be very high (e.g., 0.75) or very low (≤ 0.54). Therefore, a study design is selected wherein the sample size is adaptively determined, with a minimum value of 60 and a maximum value of 105.

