			0.2190	0.2049	0.1783	
0.70	0.9051	82.5	0.0093	0.0099	0.0133	0.2888
			0.2654	0.2287	0.1846	
0.75	0.9915	71.4	0.0005	0.0004	0.0011	0.0746
			0.5219	0.2699	0.1316	

In Table 2, the observed type I error rate (when $\phi^* = 0.54$) is 0.0239 and the average achieved sample size is 74.8. In this scenario, the trial stopped accruing at N=60 46.66% of the time (46.47% for futility, 0.19% for promising trend), at N=75 23.50% of the time (23.17% for futility, 0.33% for promising trend), at N=90 14.28% of the time (13.79% for futility, 0.49% for promising trend), and at N=105 15.56% of the time.

When $\phi^* = 0.70$, the estimated power is 0.9051 and the average achieved sample size is 82.5. In this scenario, the trial stopped accruing at N=60 27.47% of the time (0.93% for futility, 26.54% for promising trend), at N=75 23.86% of the time (0.99% for futility, 22.87% for promising trend), at N=90 19.79% of the time (1.33% for futility, 18.46% for promising trend), and at N=105 28.88% of the time. Overall, the design performs as intended, with type I error rate ≤ 0.025 , high power when $\phi^* \geq 0.68$, and smaller sample sizes when the simulated amputation-free survival rate ϕ is particularly high (e.g., $\phi^* = 0.75$) or particularly low (e.g., $\phi^* = 0.54$).

STATISTICAL ANALYSIS PLAN

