9.1.2 Sensitivity to COVID-19 deaths

By definition (Section 1), AFS includes deaths documented to be caused by COVID-19. The following additional analyses are planned to assess sensitivity of the study's conclusions to the handling of deaths related to COVID-19.

- An analysis wherein all deaths due to COVID-19 are censored on the date of death.
- A tipping point analysis in which COVID-19 deaths are included, or not, in the definition of AFS, in every combination. This analysis will use the methods of Section 6 (similar to the principal analysis) but will

STATISTICAL ANALYSIS PLAN

conduct the imputation/prediction for subjects with missing final status as if they are similar to the cohort of subjects who did not die of COVID-19. In other words, if k subjects die of COVID-19, the parameters of the piecewise exponential model in Section 6.5 (the imputation model) will be estimated while removing the k subjects who died of COVID-19, but the final posterior probability will be computed by re-inserting the COVID deaths (in separate analyses) as follows:

- k COVID deaths count as deaths at Day 180.
- $(k-1)$ COVID deaths count as deaths at Day 180, 1 counts as a non-AFS event at Day 180
- $(k-2)$ COVID deaths count as deaths at Day 180, 2 count as a non-AFS event at Day 180
- Etc.
- 0 COVID deaths count as deaths at Day 180, k count as non-AFS events at Day 180
- A frequentist competing risk survival model in which deaths due to COVID-19 are considered competing risks. Cause-specific cumulative incidence functions (CIF) will be estimated, and confidence intervals for the CIF at 180 days will be reported. The levels of confidence will be 95% (two-sided) and 97.7% (one-sided, analogous to the Bayesian posterior threshold $\psi = 0.977$).
- Other analyses suggested by patterns of observed data may be conducted.

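### SAP section 7 sets no rule for death or major amputation before wound healing; if Kaplan-Meier censors them, the proportion healed is overstated

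*SAP*

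**What the plan says.** SAP section 7 treats all secondary endpoints descriptively, with 95% confidence intervals and no hypothesis tests. Binary endpoints get a proportion with an exact binomial interval. Those "that involve the occurrence (or not) of events at times ≥ 30 days will be summarized with Kaplan-Meier time-to-event methods", with intervals on the log-survival scale.

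SAP section 3.2 gives target wound healing as "Defined as complete healing of the patient's target wound as evaluated at 30 days, 3, 6, 9 months, and 1 year"; all wound healing has the same schedule. Neither definition mentions death or amputation, and neither says whether the quantity is *ever healed by time t* or *healed at the visit*.

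Protocol section 5.9 lists among the reasons for leaving the study "instance of meeting a primary study endpoint (major amputation or death". Protocol section 11.5.1 adds a general rule: "Proportions will be calculated using known non-missing values".

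The only competing-risk method in the SAP is in section 9.1.2, for COVID-19 deaths in the primary endpoint: "Cause-specific cumulative incidence functions (CIF) will be estimated, and confidence intervals for the CIF at 180 days will be reported". Protocol section 4.6 speaks of censoring only for loss to follow-up. Protocol section 4.10.3 gives the core laboratory the assessment of healing and states no analysis rule.

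**The concern.** A subject who has died or lost the index limb can no longer heal the wound on that limb. Kaplan-Meier with that subject censored assumes that he or she would have gone on to heal at the rate of those still under follow-up. The result estimates healing in a setting without death or amputation, not the share of treated subjects who healed.

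This is a single-arm trial, and section 10.1 of the protocol names improved wound healing as the potential benefit that outweighs the procedural risk. Readers will take the healing figure as the share of treated patients who healed. SAP section 3.2 sets the objective for these endpoints as a point estimate with its precision, and both would be affected. The worse the limb and survival outcomes, the larger the overstatement.

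**Working it through.** **Inputs from the documents.** SAP section 6.7 gives daily hazards of death or major amputation of 0.005417298, 0.00647187, 0.004045362 and 0.0015350038 on days 0-30, 30-60, 60-90 and 90-180. SAP section 6.3 asks for a design that "achieves at least 80% power when AFS ≥ 0.68 and 90% power when AFS ≥ 0.70", so AFS 0.70 is the main scenario. There, SAP section 6.6 reports that "the estimated power is 0.9051 and the average achieved sample size is 82.5".

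**Inputs assumed.** True proportion healed before death or amputation by day 180: 25%, with 15% and 35% as a range. Healing hazard constant, confined to days 0-90, or starting only after day 60. Healing independent of death and amputation.

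**Step 1: reproduce the SAP's event timing.** S(t) = exp(-sum of hazard × days). The four products are 0.1625, 0.1942, 0.1214 and 0.1382, giving S(30) = 0.85, S(60) = 0.70, S(90) = 0.62 and S(180) = 0.54, as stated.

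**Step 2: scale to AFS 0.70.** Multiplying all hazards by k gives S(180) = 0.54^k, so k = ln(0.70)/ln(0.54) = 0.579. (The scaling formula printed in section 6.7, e^(-k) × 0.54, is not what these hazards imply; 0.54^k is used here.)

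**Step 3: compare the two quantities.** Let h be the healing hazard, H its integral and S_D the probability of being alive with the limb.

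- Proportion healed: the integral of h(u) × exp(-H(u)) × S_D(u) from 0 to 180.
- Limit of one minus Kaplan-Meier with death and amputation censored: the same integral without S_D(u), which equals 1 - exp(-H(180)).

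S_D is below 1 after day 0, so the second is always the larger.

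**Step 4: numbers at AFS 0.70, true 25%.**

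| Healing-time shape | H(180) solved for 25% | One minus Kaplan-Meier | Excess (points) |
|---|---|---|---|
| Constant | 0.371 | 31.0% | 6.0 |
| Days 0-90 only | 0.337 | 28.6% | 3.6 |
| After day 60 only | 0.408 | 33.5% | 8.5 |

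With a constant healing hazard, a true 25% reads 31.5% at AFS 0.68, 29.8% at 0.75 and 35.8% at 0.54. At AFS 0.70, a true 15% reads 18.7% and a true 35% reads 43.1%.

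**Step 5: interval.** The simulation used AFS 0.70, 10% uniform loss to follow-up and intervals on the log-survival scale. With a constant healing hazard, the nominal 95% interval covered the true 25% about 89% of the time at N=82 and 86% at N=105. At N=82 it was about 94% with early healing and 81% with late healing.

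**Step 6: the visit-proportion reading.** Take the constant hazard and the same exit hazard after healing. Then 0.310 × 0.70 = 21.7% of all treated subjects are healed and still in the study at day 180. If exited subjects are dropped as missing, the proportion is 21.7/70 = 31.0%. If they are kept as not healed, it is 21.7%.

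**Step 7: visit-based detection.** Table 1 of the protocol schedules wound assessment at 2 weeks and at 1, 3 and 6 months (days 14, 30, 90 and 180). Recorded healing is the sum over visits of [exp(-H(previous visit)) - exp(-H(visit))] × S_D(visit). For the constant hazard this is 0.0284 × 0.957 + 0.0315 × 0.910 + 0.1093 × 0.758 + 0.1407 × 0.70 = 23.7%. Across the three shapes it is 23.5% to 24.0%, slightly below 25%, because some subjects heal and exit before the next visit.

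**The case against.** The strongest reply is that the plan is silent rather than wrong. Section 7 does not name wound healing under Kaplan-Meier, and nothing states that death or amputation is censored. A statistician could treat healing as binary at each visit and class a subject known to have died or lost the limb as known not healed. Section 11.5.1 of the protocol is a general sentence, and section 7 of the SAP does not repeat it. This stands, and it makes the point conditional. A reader might infer that the healing rate is overstated under the plan as written. The documents do not support that: it needs the Kaplan-Meier route with censoring, or a visit proportion with exited subjects counted as missing.

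A reader might also extend the point to Rutherford change, "Defined as a change of one class or greater, as evaluated at 30 days, 3 and 6 months". That definition gives no direction of change, and no passage plans a time-to-improvement analysis, so the extension is speculative. Limb salvage and patency are different again. There the counted event is the failure, so censoring death does not inflate the success rate.

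The size rests on assumptions. The 6.0-point excess is about one standard deviation of the estimate at N=82, and coverage is near nominal if healing is early. Deaths and amputations also appear in AFS and limb salvage, so a careful reader could see them beside the healing figure. All of this bears on priority. It does not supply the missing rule.

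**Conclusion.** The gap is real and worth closing, at moderate priority. The method that best fits wound healing in section 7 comes with no competing-event rule, although death and major amputation end follow-up and rule out later healing of the index-limb wound. If they are censored, the direction of the error is certain. Its size is not: about 31% against an assumed true 25% at day 180 and AFS 0.70, or 28.6% to 33.5% across the healing-time shapes tried. That rests on an assumed healing rate, assumed shapes, independence of healing from exit, and the section 6.7 hazards. Those hazards stop at day 180, so nothing can be said about the size at 9 months or 1 year. No trial decision depends on these endpoints.

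**What to change.** In SAP section 7, state whether the healing endpoints mean *ever healed by time t* or *healed at the visit*, and then:

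- For *ever healed by time t*, replace Kaplan-Meier with the cumulative incidence function (Aalen-Johansen). Treat death and index-limb major amputation before healing as competing events, and censor only at withdrawal, loss to follow-up and end of follow-up.
- For *healed at the visit*, report the proportion with subjects who died or had a major amputation kept in the denominator as not healed. State that the non-missing rule in section 11.5.1 of the protocol does not remove them.
- State how subjects in the modified intention-to-treat population without a successful implant are counted. Protocol section 5.5 and Table 1 (footnote 10) follow them for only 30 days, and censoring them then may be informative about healing.
- Note that healing is detected at visits, so recorded healing can fall slightly below true healing.
- Kaplan-Meier may stay as a supplement, labelled as censoring death and amputation.

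The cost is a few sentences and a different procedure call on data already collected; section 9.1.2 already uses the method. The downside for the sponsor is that reported healing rates will be lower than under censoring.
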